**GSK, South Africa - Pharmacovigilance**  
**Facsimile:** 

## 12.5. Appendix 5: Clinical Laboratory Tests

- The tests detailed in [Table 1](#) will be performed by the local laboratory.
- If the local laboratory results are used to make either a study treatment decision or response evaluation, the results must be entered into the CRF.
- Protocol-specific requirements for inclusion or exclusion of participants are detailed in Section [6](#) of the protocol.
- Additional tests may be performed at any time during the study as determined necessary by the investigator or required by local regulations.

**Table 9      Protocol-Required Safety Laboratory Assessments**

Laboratory Assessments	Parameters			
Hematology	Platelet Count	RBC Indices: MCV MCH MCHC %Reticulocytes		WBC count with Differential: Neutrophils Lymphocytes Monocytes Eosinophils Basophils
	RBC Count			
	Hemoglobin			
	Hematocrit			
Clinical Chemistry 	BUN	Potassium	Aspartate Aminotransferase (AST)/ Serum Glutamic-Oxaloacetic Transaminase (SGOT)	Total and direct bilirubin
	Creatinine	Sodium	Alanine Aminotransferase (ALT)/ Serum Glutamic-Pyruvic Transaminase (SGPT)	Total Protein
	Glucose [fasting]	Calcium	Alkaline phosphatase	glucose -6-phosphate dehydrogenase (G6PD)
	Chloride	Magnesium	Lactate dehydrogenase (LD)	
Coagulation Profile	
 
• PT and aPTT
 
			
Routine Urinalysis	
 
• Specific gravity
 
• pH, glucose, protein, blood, ketones, bilirubin, urobilinogen, nitrite, leukocyte esterase by dipstick
 
• Microscopic examination (if blood or protein is abnormal)
 
			
Other Screening Tests	
 
• Breath alcohol and urine drug screen (to include at minimum: amphetamines, barbiturates, benzodiazepines, cocaine, opiates, phencyclidine (phenylcyclohexalpiperidine), tetrahydrocannabinol, methadone, methamphetamine, tricyclic antidepressants, oxycodone
 
			

Laboratory Assessments	Parameters
	
and propoxyphene)
 
 
• Cotinine
 
• Serum or urine human chorionic gonadotropin (hCG) pregnancy test (as needed for women of childbearing potential)
 
• Serology (HIV antibody, hepatitis B surface antigen [HBsAg], and hepatitis C virus antibody)] Hepatitis C RNA test for Hepatitis C antibody positive Participants
 
 
The results of each test must be entered into the CRF or equivalent.

## NOTES :

1. Details of liver chemistry stopping criteria and required actions and follow-up assessments after liver stopping or monitoring event are given in Section 8.1 and [Appendix 3](#). All events of ALT  $\geq 3 \times$  upper limit of normal (ULN) and bilirubin  $\geq 2 \times$  ULN ( $> 35\%$  direct bilirubin) or ALT  $\geq 3 \times$  ULN and international normalized ratio (INR)  $> 1.5$ , if INR measured, which may indicate severe liver injury (possible Hy's Law), must be reported as an SAE (excluding studies of hepatic impairment or cirrhosis).
2. Local urine testing will be standard for the protocol unless serum testing is required by local regulation or IRB/IEC.

## 12.6. Appendix 6: Analysis Plan

### Rules for handling decimals

The following rules will be followed with regards to the number of decimal places and presentation of data in the tables and listings of safety data:

All data will be listed according to the number of decimal places presented in the source data.

Mean and median will be tabulated to one more decimal place than the source data. Minimum and maximum values will be tabulated to the same number of decimal places as the source data.

Standard deviation (SD) will be tabulated to two more decimal places than the source data.

A maximum of three decimal places will apply to all summary statistics.

### Missing data

AEs with missing start dates/times will be handled as follows for the tabulations:

- Missing start date:
  - If the start date is completely missing but the end date is known and shows that the AE ended on or after the dosing date in a specific treatment period, then the start date will be imputed as the day of dosing in that period (therefore first dosing in the run-in period).
  - If the end date is known and shows that the AE ended before the first dosing date in the run-in period, then the screening date will be used for the start date.
  - If the end date is known and shows that the AE ended before the dosing date in the treatment period (but after dosing in the run-in period), then the first dosing date of the run-in period will be used for the start date.
  - If the end date is non-informative (i.e., is missing or does not contain enough information), the start date will be imputed as the date of first dosing in the run-in period will be used.
- Missing start day:
  - If only the start day is missing the day will be imputed as the first day on which a dose was given in that month unless the end date is known and shows that the AE ended before a dose was given in that month; in which case the date will be imputed as 01.

- If the end date is non-informative (i.e., is missing or does not contain enough information), the start date will be imputed as the first date of dosing in the known month. If the month is not a dosing month the date will be imputed as 01.
- Missing start day and month:
  - If the start day and month are missing the date will be imputed as the first day of dosing in the known year unless the end date is known and shows that the AE ended before a dose was given in that year; in which case the start day and month will be imputed as 01Jan or with the date of screening if this is later. If the end date is non-informative (i.e., is missing or does not contain enough information), the start date will be imputed as the first date of dosing in the known year. If the year is not a year of dosing then the date will be imputed as 01Jan or with the date of screening if this is later.
- Missing times
  - Missing times will be imputed as 00:00 h or with the time of dosing for events starting on a dosing day.

## **Presentation of PK Data, Descriptive Statistics and PK Assessment**

This section describes outputs to be presented.

The actual blood sampling times and time deviations will be listed for each participant dosed, treatment and scheduled sampling time. A listing of plasma concentrations of ciprofloxacin treatment will be provided.

Summary table reflecting summary statistics (n, arithmetic mean, geometric mean, median, coefficient of variation, standard deviation, minimum and maximum) per treatment will be provided for plasma concentrations of ciprofloxacin

Concentrations below the lower limit of quantification (LLOQ) will be indicated as below the limit of quantification (BLQ). These BLQ concentrations will be handled as follows:

- For descriptive statistics, pre-dose BLQ concentrations will be substituted by zeros. All other BLQ values will be substituted by  $\frac{1}{2}$ LLOQ value before the calculation of the summary statistics. Values reported as 'NS' (no sample) will be set to "missing".
- For PK assessment, all BLQ values at pre-dose and in the absorption phase, before the first reported concentration, will be substituted by zeros. The BLQ values between evaluable concentrations will be substituted by  $\frac{1}{2}$ LLOQ, before the calculation of the PK parameters. The terminal BLQ values will be set to missing. These measures are taken to prevent an over-estimation of AUC.

- For PK calculations, missing concentrations will be deleted, resulting in an interpolation between the nearest two concentration values.

A listing for PK parameters of ciprofloxacin per treatment will be provided. A summary table reflecting summary statistics (n, arithmetic mean, geometric mean, median, coefficient of variation, standard deviation, minimum and maximum) per treatment will be provided for PK parameters of ciprofloxacin.

The individual plasma ciprofloxacin concentration versus actual time profiles for each participant and treatment, as well as the mean (arithmetic and geometric) plasma ciprofloxacin concentration versus scheduled time profiles for each treatment, will be presented graphically on a linear-linear and log-linear scale. Individual plasma concentrations will be presented using actual, rather than planned, sampling times. Combined individual concentration versus time graphs per treatment will also be presented on a linear-linear scale, together with the geometric mean values. The adjusted geometric mean ratio with 90% CI will be presented graphically. The individual log-linear graphs reflecting the WinNonlin modelling results, will be presented using SAS.

The data listings, descriptive statistics, statistical analysis and graphs of this study will be generated using SAS/STAT and SAS/GRAFH software.

## **Data Precision**

The following rules will be followed with regards to the number of decimal places and presentation of data in the tables and listings concentration data.

The individual plasma concentration will be reported to the same precision as the source data (e.g., if the source data is presented to five significant digits, the individual values will be presented to five significant digits).

The mean, SD, geometric mean and median will be tabulated to one more significant digit compared to the source data, but with a maximum of four significant digits.

Minimum and maximum values will be tabulated to the same precision as the source data, but with a maximum of four significant digits.

Geometric coefficient of variation (CV) % will be presented to once decimal place.

The following rules will be followed with regards to the number of decimal places and presentation of data in the tables and listings of PK parameters.

Individual PK parameters will be presented to four significant digits, with the exception of  $t_{max}$ , which will be presented to two decimal places. In addition, PK parameters

---

 SAS Version 9.2 or higher of the SAS System. Copyright© 2002-2003. SAS Institute Inc. SAS and all other SAS Institute Inc. product or service names are registered trademarks or trademarks of SAS Institute Inc., Cary, North Carolina, USA.

directly derived from source data (e.g.,  $C_{\max}$ ) will be reported with the same precision as the source data (if this is not four significant digits).

The mean, geometric mean, median and SD values will be reported to four significant digits, all other descriptive statistics will be reported to three significant digits except for CV% which will be presented to one decimal place. For  $t_{\max}$  the minimum and maximum will be presented to two decimal places and the rest of the descriptive statistics to three decimal places.

Estimates and confidence intervals in the form of percentages will be presented two decimal places.

Source data will be used in all derived PK parameter calculations without prior rounding.

### **Analysis of Bioequivalence**

Refer to [Table 6](#).

The following SAS code will be used, with the treatments sorted in the order reference first and then test:

```
ODS OUTPUT LSMeans=lsmean estimates=est nobs=nobs Overall ANOVA=anova;  
PROC GLM DATA=pk ALPHA=0.1;  
BY Analyte Parameter;  
CLASS treatment period participant sequence2  
MODEL var= treatment period sequence participant (sequence)/ clparm;  
(where var = log [Cmax], log[AUC(0-t)])  
OUTPUT OUT=routput R=res P=pred;  
LSMEANS treatment / pdiff=control('A') CL;  
ESTIMATE 'Test versus Reference' treatment 1 -1;  
RUN;
```

---

SAS Version 9.2 or higher of the SAS System. Copyright© 2002-2003. SAS Institute Inc. SAS and all other SAS Institute Inc. product or service names are registered trademarks or trademarks of SAS Institute Inc., Cary, North Carolina, USA.

Bioequivalence of the test and reference products will be assessed on the basis of the 90% confidence intervals for estimates of the geometric mean ratios between the primary PK parameters of the test and reference products in relation to the conventional bioequivalence range of 80.00% to 125.00%.

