### 10.3.4. Analysis of Bioequivalence

**Table 7 Statistical Analysis Methods to be used for Endpoints**

Endpoint	Statistical Analysis Methods
Primary	
Following log-transformation of derived pharmacokinetic parameters <math>C_{\max}</math> and <math>AUC_{(0-t)}</math> of ciprofloxacin will be analysed by using analysis of variance with sequence, subject (sequence), treatment and period effects. Point estimates for the adjusted means on the loge scale, the mean difference between treatments and associated 90% CIs for the difference Treatment A - Treatment B will be constructed using the residual variance.
 
These point estimates and confidence intervals will then be exponentially back-transformed to obtain adjusted (least square) geometric means for each treatment and point estimates and associated 90% confidence intervals for the ratio, Treatment A/Treatment B.
 
Distributional assumptions underlying the statistical analyses will be assessed by visual inspection of residual plots. Normality will be examined by normal probability plots, while homogeneity of variance will be assessed by plotting the residuals against the predicted values for the model. If the assumptions are

Endpoint	Statistical Analysis Methods
	seriously violated then alternative statistical methods will be considered.
Secondary	AUC (0-∞) of ciprofloxacin will be analysed as per primary analysis; t max of ciprofloxacin will be analysed using a nonparametric test to compute point estimate of the median and associated 90% confidence intervals for the median differences, Treatment A –Treatment B %AUCex will not be statistically analysed. A summary will be created. For t½ the n, median, minimum, and maximum values will be presented

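### Appendix 6 orders the treatments reference first but codes the primary contrast as if Test came first, so the Test/Reference ratio is inverted if the stated order is applied

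*Combined protocol and SAP*

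**What the plan says.** The intended direction is fixed outside the code. Section 7.3 defines Treatment A as Test (GR37547) and Treatment B as Reference (Ciproxin). Section 10 (Bioequivalence) frames the hypotheses and the decision rule on the ratio of test to reference geometric means. Table 7 in Section 10.3.4 asks for "90% CIs for the difference Treatment A - Treatment B will be constructed using the residual variance", and after back-transformation for point estimates and "associated 90% confidence intervals for the ratio, Treatment A/Treatment B".

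Appendix 6 (Analysis of Bioequivalence) prints the code for this analysis:

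- The introductory sentence says it is run "with the treatments sorted in the order reference first and then test".
- The procedure line is "PROC GLM DATA=pk ALPHA=0.1". No `ORDER=` option is printed.
- The contrast is "ESTIMATE 'Test versus Reference' treatment 1 -1".
- The least-squares means line is "LSMEANS treatment / pdiff=control('A') CL".
- The saved outputs are set by "ODS OUTPUT LSMeans=lsmean estimates=est nobs=nobs Overall ANOVA=anova".

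**The concern.** ESTIMATE coefficients attach to the levels of the factor in their order. Coefficients 1 and -1 mean first level minus second level. If Reference is first, as the introductory sentence says, the line labelled as Test versus Reference computes Reference minus Test. The sentence and the line that follows it therefore disagree, and a programmer who puts the sentence into effect also departs from Table 7.

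At stake is the direction of the primary estimate. A test product with lower exposure than the reference would be reported as having higher exposure, under a label that says otherwise, in the primary results table and in the planned figure of the adjusted geometric mean ratio. The pass or fail result would not reveal the error, because it is the same in either direction.

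**Working it through.** **1. The plan's own figure.** Section 10.1 gives CV 18%, ratio 0.95, limits 80.00% to 125.00%, alpha 0.05 and power 90%, with 22 evaluable participants. Exact power of the two one-sided tests procedure for a 2x2 crossover (log scale, n - 2 df) is 89.9% at n = 20 and 92.4% at n = 22. So 22 is the smallest balanced number reaching 90%, and the planning inputs reproduce. Power is the same 92.4% at a true ratio of 1/0.95.

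**2. What the code gives under each reading.** ESTIMATE is first level minus second level. LSMEANS with `control('A')` is always B minus A. T is Test and R is Reference.

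| Coding | Level order | Stated order met? | ESTIMATE | LSMEANS difference |
|---|---|---|---|---|
| A = Test (Section 7.3) | A, B | No | T - R | R - T |
| A = Test (Section 7.3) | B, A | Yes | R - T | R - T |
| A = Reference (recoded) | A, B | Yes | R - T | T - R |
| A = Reference (recoded) | B, A | No | T - R | T - R |

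Whenever Reference is the first level, ESTIMATE is reversed. In no row do the stated order, ESTIMATE and the LSMEANS difference all agree with Test minus Reference. The two recoded rows also contradict Section 7.3; they are listed only to show that recoding does not remove the conflict.

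**3. Which row applies.** The printed code does not settle this. With no `ORDER=` option, I assume the software orders levels by value. Sorting the data set alone then leaves the order A, B (first row), and ESTIMATE is correct. Reaching the second or third row needs an `ORDER=` option or a recoding, and neither is printed.

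**4. Size of an inversion at the planning values.**

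- Within-participant SD on the log scale: s = sqrt(ln(1 + 0.18²)) = 0.1786.
- Half-width of the 90% CI: h = t(0.95, n - 2) × s × sqrt(2/n).
  - n = 22: 1.7247 × 0.1786 × 0.3015 = 0.0929.
  - n = 26: 1.7109 × 0.1786 × 0.2774 = 0.0847.
- Planned CI: 0.95 × exp(±h). Inverted result: the reciprocal, with the limits swapped.

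| n | Test/Reference as planned | Reported if inverted |
|---|---|---|
| 22 | 95.00% (86.58% to 104.24%) | 105.26% (95.93% to 115.51%) |
| 26 | 95.00% (87.28% to 103.40%) | 105.26% (96.71% to 114.57%) |

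**5. Effect on the decision.** Since 1/0.80 = 1.25, an interval lies inside 0.80 to 1.25 exactly when its reciprocal does. Near the lower limit at n = 22, an estimate of 88.00% (80.20% to 96.56%) inverts to 113.64% (103.56% to 124.69%). Both pass.

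**The case against.** The strongest reply is that the code may well run correctly. Under the protocol's treatment codes and value-ordered levels, ESTIMATE gives A minus B as Table 7 requires, and the ordering sentence may describe only how the data set is sorted. Inversion then needs code that the plan does not print. This stands, and it is why the numerical consequence is conditional. It does not reconcile the text: the sentence would then describe an order that the model does not use, and a correct result would rest on a software default rather than on the plan.

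The intended direction is also not in doubt, and an inverted ratio should be noticed. Table 7 requires the back-transformation "to obtain adjusted (least square) geometric means for each treatment", and Appendix 6 also asks for descriptive geometric means of the PK parameters by treatment. Either set would contradict a reversed ratio. This stands and limits the risk.

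The LSMEANS control carries little weight alone. The ODS OUTPUT line names no table of LSMEANS differences, so `control('A')` is not shown to feed a reported result. That also stands. Finally, the printed block needs some adaptation before it will run, though part of this may come from text extraction, so not too much should be inferred from what it omits.

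**Conclusion.** The inconsistency holds as a matter of text: the stated order and the ESTIMATE coefficients cannot both be right if the estimate is to be Test minus Reference. It is minor. If the stated order takes effect as the level order, the primary ratio and 90% CI are reported as reciprocals, for example 105.26% in place of 95.00% at the planned ratio. If levels are ordered by value with the protocol's codes, the error in ESTIMATE is zero. The bioequivalence conclusion, type I error, power and sample size are unaffected in both cases. Confidence is high for the mismatch in the text; no claim is made that a result would in fact be misreported. The intervals assume the planning values of Section 10.1 and the 2x2 crossover residual variance with n - 2 degrees of freedom.

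**What to change.** State one level order in Appendix 6 and make the code follow it. Either of these works:

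- Order the levels A then B, keep coefficients 1 and -1, and delete the sentence that puts the reference first.
- Enforce Reference first explicitly in the code and change the coefficients to -1 and 1.

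In both cases, set the LSMEANS control to the Reference level, which is `control('B')` under the protocol's codes.

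As a separate clerical correction, the pointer at the head of this part of Appendix 6 goes to Table 6 (analysis populations) and should go to Table 7 (analysis methods).

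The cost is one phrase, a few tokens of code and one cross-reference. Sample size and study conduct do not change.

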## 10.1. Sample Size Determination

Sample Size Rationale:

Bioequivalence is to be determined on the basis of the endpoints  $C_{max}$  and  $AUC_{(0-t)}$  of ciprofloxacin.

Intra participant coefficient of variation ( $CV_w$ ) estimates in recent published data for ciprofloxacin were in the range of 12 to 18% for the primary endpoints of ciprofloxacin [Hassan, 2007; Cuadrado, 2004] which are in line with older published data [Galicia, 1998]. For the oral formulation,  $AUC$  data ( $CV_w$  approximately 11-12%) generally were less variable than  $C_{max}$  data (15-18%) and thus the latter should be considered for sample size calculation.

Hence, the sample size for this trial was determined based on maximum observed intra participant CV of 18%.

Based on a BE range of 80.00% to 125.00% for  $C_{max}$  and  $AUC_{(0-t)}$ , for ciprofloxacin assuming intra participant CV to be 18% and a "test/reference" mean ratio of 0.95; 22 evaluable subjects are needed to achieve a power of 90% at an alpha level of 0.05 for the single test for testing BE.

Approximately 26 eligible participants (approximately 19% in excess of number needed to complete) will be entered into the study to complete the study with at least 22 evaluable participants. See Section 5.2

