### **Tables**

Demographic characteristics

Statistical analyses of ciprofloxacin PK parameters (ANOVA)

Non Parametric Analysis of ciprofloxacin PK parameter

Plasma ciprofloxacin concentration (unit)

Plasma ciprofloxacin PK parameter (unit)

Adverse events summary by treatment

Concomitant Medication summary by treatment

Summary Statistics of Vital Signs Values

Summary Statistics of Chemistry Values.

Summary Statistics of Haematology Values.

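### The SAS code's default sequence F-test and its 90% limits for each product's mean use within-participant error only; the bioequivalence interval is not affected

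*Combined protocol and SAP*

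**What the plan says.** Appendix 6 (Analysis Plan), under Analysis of Bioequivalence, sets out the SAS code to be used. The procedure call is "PROC GLM DATA=pk ALPHA=0.1", the model is "MODEL var= treatment period sequence participant (sequence)/ clparm", and the treatment means are requested with "LSMEANS treatment / pdiff=control('A') CL". An ESTIMATE statement gives the treatment contrast. There is no RANDOM statement and no TEST statement. The ODS OUTPUT line names four tables to be saved: the least-squares means, the estimates, the number of observations and the overall ANOVA.

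Table 7 in section 10.3.4 describes the same model in words, as "analysis of variance with sequence, subject (sequence), treatment and period effects". The 90% confidence intervals "for the difference Treatment A - Treatment B will be constructed using the residual variance". Table 7 asks for point estimates of the adjusted means and for intervals on the difference and the ratio. It does not ask for an interval on each product's mean.

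Section 10 and Appendix 6 both rest bioequivalence on the 90% CI for the ratio lying within 80-125% for both primary parameters. Neither mentions a sequence hypothesis. The planned outputs include a table whose title begins "Statistical analyses of ciprofloxacin PK parameters (ANOVA" and, among the listings, one named *Statistical output*.

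**The concern.** In an AB/BA crossover each participant belongs to one sequence, so two sequences are compared by comparing two groups of people. Chance differences between those groups reflect between-participant as well as within-participant variance. When participant(sequence) is an ordinary model term and no other error is named, GLM divides the sequence mean square by the residual, which holds only within-participant variance. The F-test is then too large on average whenever participants differ from one another, even with no true sequence effect.

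The same shortfall affects the limits that CL produces for each product's mean: they describe within-participant error alone and are too narrow.

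What is at stake is interpretation. The sequence line is where a reader of a two-period crossover looks for unequal carry-over or unequal groups. A spurious small p-value there could raise avoidable questions about a sound result, and the per-product limits would overstate precision if anyone quoted them.

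**Working it through.** **Inputs from the documents.** Section 10.1: within-participant CV 18% for sample size, and about 11-12% for AUC; ratio 0.95; 22 evaluable participants; 90% power; alpha 0.05. Table 5: 13 per sequence, 26 in all. Appendix 6: 90% limits (ALPHA=0.1).

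**Assumptions, not in the documents.** Between-participant CV, varied over 15-40%; a nominal 5% level for the sequence test; no true sequence effect.

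**The plan's own figure first.** Exact two-one-sided-tests power for a 2x2 crossover on the log scale, with σw² = ln(1 + 0.18²) = 0.0319, standard error σw√(2/N) and N − 2 degrees of freedom, is 89.9% at N = 20, 92.4% at N = 22 and 95.8% at N = 26. The smallest balanced N that reaches 90% is 22, so the stated number reproduces.

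**Sequence test.** With no sequence effect, the sequence mean square has expectation σw² + 2σb², and the residual has expectation σw². The F-ratio as coded is therefore inflated by k = 1 + 2σb²/σw², and

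false-positive rate = P[F(1, 20) > 4.351/k], where 4.351 is the 5% critical value of F(1, 20).

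Example: at a between-participant CV of 30%, σb² = ln(1 + 0.30²) = 0.0862. With CVw 18%, k = 1 + 2(0.0862)/0.0319 = 6.4, the effective cut-off is 4.351/6.4 = 0.68, and the rate is 42%.

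**Limits on each mean.** The code's standard error squared is MSE/n, while the true variance is (σw² + σb²)/n. The true standard error is larger by r = √(1 + σb²/σw²), so coverage is P[|t(20)| < 1.725/r]. In the same example r = √(1 + 0.0862/0.0319) = 1.92, and coverage is 62%.

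| Between-participant CV (assumed) | False-positive rate, CVw 18% | False-positive rate, CVw 12% | Coverage of 90% limits, CVw 18% | Coverage of 90% limits, CVw 12% |
|---|---|---|---|---|
| 15% | 19% | 32% | 80% | 71% |
| 20% | 28% | 42% | 74% | 62% |
| 25% | 35% | 51% | 68% | 54% |
| 30% | 42% | 57% | 62% | 48% |
| 40% | 52% | 66% | 52% | 39% |

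Using 26 participants instead of 22 changes the false-positive rates by less than one point. Even a between-participant CV of 10% gives 12% (CVw 18%) and 19% (CVw 12%). If the sequence p-value were read at 10% instead of 5%, the rates over the 15-40% range would be about 28-60% with CVw 18%.

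**Simulation check (20,000 trials per setting, n = 22).**

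| CVw, between CV | Sequence test as coded | Sequence tested against participant(sequence) | Coverage of 90% CI for the treatment difference |
|---|---|---|---|
| 18%, 20% | 27.2% | 5.0% | 89.7% |
| 18%, 30% | 41.7% | 5.2% | 90.3% |
| 18%, 40% | 52.8% | 5.2% | 90.0% |
| 12%, 20% | 42.0% | 5.0% | 90.2% |
| 12%, 30% | 56.3% | 4.9% | 89.6% |

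The correct error term restores the 5% level. The interval for the treatment difference holds its 90% coverage under the code as written, because the difference is a within-participant contrast and the residual is its proper error.

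**The case against.** The strongest reply is that nothing in the plan depends on these numbers. No section states a sequence hypothesis, a significance level for one, or a decision that uses it. Table 7 describes inference on the treatment difference only, and the planned interval figure shows the ratio. All of that stands.

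A reader might infer that the planned ANOVA table will show a false sequence effect. The documents do not establish this. The ODS line saves the overall ANOVA, which has model, error and total rows; the per-effect tests are a separate table that it does not name. The limits on each mean are likewise separate from the saved table of least-squares means. The wrong values would therefore most likely surface only in the *Statistical output* listing.

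A reader might also take some single false-alarm rate as a property of this trial. It is not one: each rate above needs a between-participant CV and a test level that the documents do not supply. Only the direction is free of that assumption.

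Finally, carry-over can be judged more directly. The washout is at least 7 days, against a half-life of 4-7 hours (section 3.2), which is at least 168/7 = 24 half-lives. A pre-dose sample is taken in each period, and section 10.3.1 has a rule for pre-dose values above 5% of Cmax. This weakens the practical harm of a false sequence signal.

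What survives is that the plan commits to this code, and the code yields an invalid test and too-narrow limits that can reach a planned listing of the study report.

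**Conclusion.** The point holds as a minor correction. As written, the code's default sequence F-test uses the wrong error term, and its nominal 90% limits on each product's mean omit between-participant variance. For an assumed between-participant CV of 15-40%, 22 participants and a 5% level, false rejection is about 19-52% at CVw 18% and 32-66% at CVw 12%. Coverage of the limits falls to about 80-52% and 71-39%. Any positive between-participant variance gives the same direction of error.

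A stronger conclusion, that the bioequivalence result is at risk, is not supported. This point leaves the ratio, its 90% CI, the decision rule, the power and the sample size unchanged.

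**What to change.** Add to the code `TEST H=sequence E=participant(sequence) / HTYPE=3 ETYPE=3;` and, if a sequence p-value is shown at all, report only that one. Do not report the per-product limits from LSMEANS; if they are wanted, take them from a model with participant random. Dropping CL loses nothing that Table 7 asks for, because CLPARM on the MODEL statement already gives the limits for the ESTIMATE contrast. Keep the residual-based 90% CI for the ratio.

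The cost is one or two lines of code and a sentence in Appendix 6, made before the analysis is run. The primary analysis does not change.
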